Subjects will be randomized 1:1 to either active or sham RS-tDCS. The active RS-tDCS delivers a constant current intensity of 2mA on the subject's scalp, with SNAPstrap headgear and 5x7 (35cm2) SNAPpads positioning bilaterally (anodal-left and cathodal-right), on the DLPFC, for 30 minutes. A similar protocol's administration was found effective, safe, and tolerable as an add-on intervention to decrease depressive symptoms in patients with bipolar depression (45). Sham tDCS looks identical to a typical RS-tDCS cap but delivers a 30-second ramp-up (0-2 mA) stimulation followed by a 30-second rampdown (2-0 mA) at the beginning and end of the application. Figure 2 shows a representation of the electric current delivered by the active and sham RS-tDCS.

[figure not shown]

Figure 2. Stimulation protocol. Active tDCS (upper) and sham tDCS (lower).

The tolerability and safety of home-based tDCS were assessed over 6,779 sessions from six clinical trials. Sessions were administered daily, with treatment ranging from 10 to 60 sessions per subject. The authors reported no serious adverse events, a similar proportion of tingling (68%), itching (41%), and warmth sensation (42%) between active and sham groups, and no participant discontinuation due to lack of tolerability (39).

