16. DATA AND SAFETY MONITORING PLAN

Risk to study subjects is minimized by only employing well-trained and clinically experienced personnel. Routine hospital protocols are already in place for handling in-person and over-the-phone crises.

Adverse Events (AEs) and Serious Adverse Events (SAEs)

An adverse event is "any untoward or unfavorable medical occurrence in a human subject...temporally associated with the subject's participation in the research, whether or not considered related to the subject's participation in the research." A serious adverse event (SAE) is an event where a relationship to the research study cannot be ruled out, and the event is life-threatening/results in death OR disabling/incapacitating OR requires or prolongs hospitalization OR involves an overdose OR was otherwise unanticipated, related to the study procedures. Due to the nature of this study, suicide attempts and psychiatric hospitalizations are possible to

happen during its course. These events are considered SAEs and reported as such. In most circumstances, suicide attempts and psychiatric hospitalizations are expected for this population and, as a result, non-study related. As such, these SAEs will be reported at continuing review but only unexpected reported immediately to the IRB. Suicide deaths are reported to the IRB within 48 hours of learning of the death. In addition, the report includes investigators' judgment as to whether a relationship to the research study can/cannot be ruled out.

For all AEs, the date and time of onset and outcome, course, intensity, action is taken, and causality to study treatment will be assessed. Based on the review of the circumstances and as-needed consultation with co-investigators, the PI can reclassify an AE as an SAE. If considered related to the study, unanticipated adverse events involving risks to subjects or others will be reported by the PI to IRB. For each adverse event, the treatment groups are compared in a pair-wise fashion regarding the occurrence of at least one event using Fisher's exact tests; the numbers of individual events will also be described. All subjects are included in these analyses.

Confidentiality

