17. DATA ANALYSIS PLAN

To assess feasibility, the primary outcome of this study, we chose a sample size of 20. To infer feasibility, at least 50% of the sessions should be performed successfully per subject for at least 70% of the subjects. This criterion is based on a study that reported dropout rates between 22% and 25% of home-based tDCS for patients with bipolar depression (40) and that therapeutic effects with tDCS could be achieved within one week of treatment (24). For each time point established, we will compare groups with a t-test or chi-square test, for continuous and categorical data, respectively (a p value<0.05 will be considered significant).

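### The chi-square test for suicidal ideation relapse leaves the continuity correction and small-count rule unspecified in 20 subjects, so significance can turn on a software option

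*Combined protocol and SAP*

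**What the plan says.** Section 17 (Data Analysis Plan) gives one sentence on between-group testing: "For each time point established, we will compare groups with a t-test or chi-square test, for continuous and categorical data, respectively", with the threshold "a p value<0.05 will be considered significant". It does not say whether the chi-square statistic carries a continuity correction, or what happens when expected counts are small.

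The size is fixed in the same section ("we chose a sample size of 20"). Section 4.1 adds "Subjects will be randomized 1:1 to either active or sham RS-tDCS", so about 10 per arm at entry. Section 17 also cites "dropout rates between 22% and 25% of home-based tDCS for patients with bipolar depression", as support for the feasibility criterion.

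The main categorical outcome that this sentence governs is secondary outcome 3 in section 4: the proportion answering no to C-SSRS questions 1 and 2 at days 14, 30 and 60, from which relapse is read.

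For adverse events, section 16 states that "the treatment groups are compared in a pair-wise fashion regarding the occurrence of at least one event", using Fisher's exact tests and including all subjects.

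**The concern.** The chi-square test relies on a large-sample approximation, and the usual guard is a minimum expected count of 5. With 20 subjects in two arms that guard fails almost always. The plan neither names the corrected or uncorrected version nor provides a fallback.

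Two things are at stake. First, under one reading of the plan, p<0.05 is not reliably a 5% test. Second, the corrected and uncorrected versions can disagree about significance on identical data, so the result may depend on a software default. Preventing relapse is the intervention's stated purpose (section 1, Aim 1), and a p-value whose definition is open until analysis is of little use there.

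**Working it through.** **Inputs.** From the documents: total 20, allocation 1:1, threshold 0.05, chi-square test (section 17), Fisher's exact test for adverse events (section 16). Assumed: the numbers analysed per arm and the common relapse rate, neither of which the documents give. Applying the cited 22-25% loss to assessments would leave 20 × 0.78 = 15.6 to 20 × 0.75 = 15. The plan has no power or attained error rate to reproduce.

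**Expected counts.** With n₂ in the smaller arm, N in total and m events, the smallest expected count is n₂ × min(m, N−m)/N. Since min(m, N−m) ≤ N/2, this is at most n₂/2. It is therefore below 5 whenever the smaller arm has fewer than 10. At 10/10 it reaches 5 only when m = 10.

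**One table, three answers.** Take 8 per arm with 0 v 4 relapses:
- Uncorrected: X² = 16 × (0×4 − 4×8)² / (8×8×4×12) = 16 × 1024/3072 = 5.33, p = 0.021.
- Yates: 16 × (32 − 8)²/3072 = 3.00, p = 0.083.
- Fisher: 2 × C(8,4)/C(16,4) = 2 × 70/1820 = 0.077.

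At 10 per arm, 0 v 4 gives 0.025, 0.094 and 0.087 in the same order, and 1 v 6 gives 0.019, 0.061 and 0.057. The disagreement therefore does not need dropout.

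**Type I error.** For each pair of arm sizes, all 2×2 tables were listed, each was marked as rejecting or not at p<0.05, and the binomial probabilities of the rejecting tables were summed for a common rate from 0.005 to 0.995. A hand check at 8/8, rate 0.5: the uncorrected test rejects 0 v ≥4, 1 v ≥5, 2 v ≥6, 3 v ≥7, 4 v 8 and their mirror images. The weights C(8,a) × C(8,b) sum to 163 + 744 + 1036 + 504 + 70 = 2517, and 2 × 2517/2¹⁶ = 7.7%. Fisher does not reject 0 v 4, 1 v 5, 2 v 6, 3 v 7 or 4 v 8 (weight 70 + 448 + 784 + 448 + 70 = 1820), leaving 2 × 697/2¹⁶ = 2.1%.

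| Arms | Largest error, uncorrected | Common rates where it exceeds 5% | Largest error, Fisher |
|---|---|---|---|
| 10/10 | 4.2% | none | 1.3% |
| 11/9 | 5.7% | 0.18-0.82 | 2.8% |
| 10/9 | 6.5% | 0.19-0.81 | 2.1% |
| 8/8 | 7.7% | 0.29-0.71 | 2.1% |
| 9/7 | 8.1% | 0.20-0.80 | 2.5% |
| 10/6 | 5.7% | 0.37-0.63 | 2.8% |
| 8/7 | 4.7% | none | 3.5% |
| 9/6 | 4.3% | none | 3.5% |
| 10/5 | 5.0% | none | 2.8% |

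With Yates' correction the largest value at any size checked is 2.1%. If each subject is lost at random with probability 22-25%, the uncorrected error averaged over the resulting arm sizes is 1.2-1.3% at a common rate of 0.10, 3.6-3.8% at 0.20, 5.1-5.2% at 0.30 and 5.8% at 0.50.

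**Power.** The same sum, with relapse rates of 50% v 10% (assumed), gives 43.6% uncorrected and 21.7% with Fisher at 8/8, and 47.1% and 29.5% at 10/10. An unconditional exact test was enumerated too (Boschloo's: tables ranked by Fisher p-value, with the p-value being the largest probability, over the common rate, of a table at least as extreme). Its power is 33.5% at 8/8 and 47.1% at 10/10, with error held below 5%.

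**The case against.** Several points on the other side stand.

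- The excess belongs to the uncorrected statistic only. The plan does not say uncorrected, and a corrected test is conservative.
- A reader might infer that the plan's own expected dropout pushes the test above 5%. The documents do not support that. The 22-25% is an external figure cited for the feasibility criterion. Stopping sessions is not the same as missing an assessment: the assessments are timed from the first session (section 8) and paid for separately (section 12). Even at 25% loss, 15 analysed shows no excess.
- A reader might take 7.7% or 8.1% as the actual error rate. These are maxima over an unknown relapse rate. At 8/8 the error is 4.0% at a rate of 0.25 and 0.5% at 0.10, and averaged over random dropout the excess is under one percentage point.
- A reader might call 0 v 4 at 8/8 a false positive. That goes too far: Boschloo's test gives p = 0.028 there. It does not support 1 v 5 (0.053) or 2 v 6 (0.077), which the uncorrected test also calls significant (0.039 and 0.046). The example shows dependence on the test chosen, not which answer is true.
- A reader might see sections 16 and 17 as contradictory. They cover different outcomes, and using different tests is allowed.
- The reach is narrow. Feasibility and acceptability are judged on all subjects against fixed percentages, blinding uses the Bang index, and Hypothesis 2 concerns ideation intensity rather than relapse.
- Fisher's test has a real cost in power, which matters in a pilot seeking a preliminary signal.

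None of this settles which test section 17 specifies. That gap is in the text and needs no assumption about dropout or relapse.

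**Conclusion.** The point holds in a limited form. Section 17 leaves the categorical test undetermined at a size where its approximation is unsupported in nearly every possible table, and the choice left open can move a result across p = 0.05 even at 10/10.

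If the uncorrected version is used, the error rate can exceed 5%, by up to about 3 percentage points (8.1% at 9/7), at some arm sizes and middling relapse rates. It does not do so at 10/10, with 15 analysed, or at low relapse rates. The arm sizes and rates are assumptions. In particular, 11/9 assumes that allocation is not forced to be equal; the sections available describe no blocking.

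Severity is minor: a secondary outcome in a pilot trial, with a cheap remedy.

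**What to change.** In section 17, replace the chi-square test for 2×2 group comparisons with one named exact test, fixed before unblinding. Fisher's exact test would match section 16. An unconditional exact test such as Boschloo's also controls the error and loses less power. Report the difference in proportions with an exact 95% confidence interval as the main result at each time point, with the p-value second; this suits Aim 2, which is to inform a later trial's sample size.

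The change is one phrase and one added sentence. The cost is lower power than the uncorrected test. At an assumed 50% v 10% relapse, Fisher's test falls from about 44% to 22% at 8/8 and from 47% to 30% at 10/10. Boschloo's falls to about 34% at 8/8 and loses nothing at 10/10, at the price of slightly more computation and a less familiar method.

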suicides per 100,000 person-years soon after hospital discharge among U.S. Army soldiers, almost 14-fold higher compared with the total U.S. Army. Previous suicidal behavior was one of the main predictors (OR=2.9) (34). Forte el al. (2019) addressed suicidal risk after hospital discharge in a review paper that included 48 studies with a total of 1,700,785 participants followed for almost 8 years after a psychiatric hospitalization (35). The authors noted that about 20% of the suicides and attempts had occurred within 15 days following hospital discharge and more than a quarter in the first month. The results also showed that mood disorders were associated with the highest risk (35).

These studies clearly show that evidence-based interventions for suicidal behavior prevention offered soon after psychiatric inpatient hospitalization are of major significance, especially for high-risk groups such as individuals with a history of SI and behavior and mood disorders. However, the low rate of outpatient treatment engagement and the high rate of dropout from an outpatient service after discharge from an emergency department is a challenge (36), and speaks to the need to overcome these barriers to care. Effective tDCS stimulation requires daily sessions, typically performed in an outpatient clinic. For some patients, this presents a serious barrier. Specifically, for patients in the first weeks after discharge, residual symptoms, and the need to reorganize personal issues and obligations after a period at the hospital may prevent them from commuting to daily visits at health facilities to complete a non-invasive brain stimulation treatment. Thus, to address low treatment engagement and overcome barriers to care with this population, this study will test the feasibility of a home-based tDCS protocol for preventing SI relapse soon after hospitalization discharge.

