1. Intensity of suicidal ideation as assessed by the Columbia Suicide Severity Rating Scale (C-SSRS) (41) (time frame: day 14 [+ 7 days], day 30 [+ 7 days], and day 60 [+ 10 days] from the first RS-tDCS session):

The C-SSRS is a suicidal ideation and behavior rating scale with yes/no responses. For each of the 5 items of the C-SSRS related to suicidal ideation intensity, an individual's degree of suicidal ideation is rated on a 0-5 scale. The total score is the sum of the 5 intensity item scores (total score ranges from 0 to 25), with higher scores indicating more severe suicidal ideation.

2. Acceptability based on subject's readiness, self-confidence, and satisfaction in dealing with the device and RS-tDCS sessions. Acceptability based on subject's readiness, self-confidence, and satisfaction will be considered if at least 60% of all subject's rate "strongly agree" or "agree" on the questionnaire item 11: "Overall, I felt that transcranial electrical stimulation treatment benefited me" (the questionnaire is a 5-item Likert scale with the following response options "Strongly agree", "Agree", "Neither agree nor disagree", "Disagree", "Strongly disagree") (42). These questions were adapted from other studies with home-based tDCS (37, 43) and will be presenting as following: 1) "It was easy to prepare the device and accessories"; 2) "I felt confident setting up the stimulation sessions"; 3) "I felt confident using the device"; 4) "I needed to learn a lot of things before I could get going with this device"; 5) "The device was unnecessarily complex"; 6) "I could find a convenient time to do the stimulation sessions"; 7) "I would imagine that most people would learn to use this device quickly"; 8) "The stimulation sessions interfered with my everyday life"; 9) "It would have helped to have more in-person, one-on-one instruction"; 10) "I felt that the remote supervision sessions were helpful"; 11) "Overall, I felt that transcranial electrical stimulation treatment benefited me". Questions 4, 5, 8, and 9 will be reverse coded. This information will be collected after the final RS-tDCS session (that is, the tenth RS-tDCS session).15

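### Separate t-tests at each visit ignore leavers' earlier RRS, CAST and MADRS scores, so the day 30 and day 60 arm differences may be biased if exit follows worsening

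*Combined protocol and SAP*

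**What the plan says.** RRS, CAST and MADRS are secondary outcomes in Section 4, collected at baseline and then at "day 14 [+ 7 days], day 30 [+ 7 days], and day 60 [+ 10 days] from the first RS-tDCS session". Section 17 gives the between-arm analysis in one sentence: "For each time point established, we will compare groups with a t-test or chi-square test, for continuous and categorical data, respectively", with the rule that "a p value<0.05 will be considered significant". It names no analysis set, missing-data rule, repeated-measures model or sensitivity analysis for these comparisons. The only statement about who is analysed, in Section 16, concerns adverse events.

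On size, Section 17 says "we chose a sample size of 20", for feasibility, and Section 4 says "Subjects will be randomized 1:1 to either active or sham RS-tDCS", so 10 per arm. Section 17 also cites "dropout rates between 22% and 25% of home-based tDCS for patients with bipolar depression", as a basis for the session-completion criterion.

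Section 13 allows removal of subjects who seem to be harmed by taking part, and requires it for those who start electroconvulsive therapy or transcranial magnetic stimulation. It stops the gathering of new identifying information after withdrawal, but lets information already gathered be used.

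**The concern.** A two-sample t-test at day 60 can use only subjects scored at day 60, unless values are imputed, and no imputation is planned. It treats those who left as being like those who stayed in the same arm. Two of the removal routes in Section 13 could well follow a worsening of mood, so that assumption is doubtful. Day 14 and day 30 scores that help to predict the missing ones are in the database, and the later tests ignore them.

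At stake are the day 30 and day 60 differences on three prespecified scales, which show whether any effect lasts. The direction of error is not fixed. If worsening sham subjects leave, the remaining sham group looks too well and a benefit is understated. If worsening active subjects leave, a benefit is overstated. Adjusting each visit for baseline would not solve this, because scores from the visits in between would still be ignored.

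**Working it through.** Section 17 states the sample size as a choice, with no effect size, SD or power for any comparison of arms, so there is no planned figure to reproduce.

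**Inputs from the documents:** 20 subjects, 1:1, three post-baseline visits, a t-test at each.

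**Assumed, because the documents give no values:** SD 1 at each visit; between-visit correlation 0.5 or 0.7; true difference (active minus sham, negative is benefit) of 0 or −0.5 SD at every visit; all loss after day 14, reaching about 22% by day 60 in an arm with sham-level scores; exit by a logistic model with slope 1 or 2 per SD.

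**1. Sampling SD of the difference.** With everyone seen, √(2/10) = 0.45. With about 8 per arm left, √(2/8) = 0.50.

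**2. Where bias comes from.** If a proportion p of an arm is missing and the leavers' mean would have been g worse than the stayers' mean, the observed mean is too low by p × g. So

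bias of (active − sham) = p_S × g_S − p_A × g_A.

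Equal p and g in both arms give zero. Random exit in one arm makes its g zero, and the other arm's term remains.

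**3. Day 60 in a large-sample simulation, exit driven by the last observed score.**

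| Exit follows worsening in | True difference | t-test estimate | Bias |
|---|---|---|---|
| Both arms alike | 0 | 0.00 | none |
| Both arms alike | −0.5 | −0.42 to −0.47 | 0.03 to 0.08, benefit understated |
| Sham only (slope 2) | 0 | 0.15 to 0.21 | 0.15 to 0.21, against active |
| Sham only (slope 2) | −0.5 | −0.29 to −0.34 | 0.16 to 0.21, benefit understated |
| Active only (slope 2) | 0 | −0.16 to −0.21 | 0.16 to 0.21, for active |
| Active only (slope 2) | −0.5 | −0.59 to −0.62 | 0.09 to 0.12, benefit overstated |

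The last row is smaller because fewer active subjects leave (12%) when they are doing better. At day 30 the one-arm bias with no true effect is 0.08 to 0.12 SD. A likelihood-based estimate that uses all visits is within 0.01 SD of the truth in every row.

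Step 2 shows what the one-arm figures require. With p = 0.22, a bias of 0.15 means g = 0.15/0.22 = 0.68. With p = 0.21, a bias of 0.21 means g = 0.21/0.21 = 1.0. Leavers would have to be about 0.7 to 1.0 SD worse than stayers.

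**4. Trials of 10 per arm.** With sham-only exit at slope 1.5, t-test bias is 0.14 to 0.19 SD, and the unstructured repeated-measures model's is 0.03 or less. The spread of both estimates is 0.49 to 0.51 SD. With steeper exit the t-test bias reaches 0.28 SD.

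**5. Exit driven by the score not yet seen.** With one-arm exit and no true effect, t-test bias is 0.23 to 0.25 SD and the all-visit estimate's is 0.10 to 0.15. With the same mechanism in both arms and a true −0.5, the estimates are −0.40 to −0.45 and −0.43 to −0.47. The model reduces this bias but does not remove it.

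**The case against.** The strongest reply is one of proportion. This is a 20-subject feasibility pilot whose primary outcome is session completion. The bias is smaller than the sampling SD of about 0.5, and an unstructured covariance is fragile with 10 per arm. That stands, and it limits the importance of the point. It does not remove it: the bias is systematic, and the remedy costs almost nothing in precision.

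Several stronger readings are tempting, and the documents do not support them.

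- **That leavers' scores are lost.** They count at the visits attended, and Section 13 keeps data already gathered.
- **That the later differences are biased.** This is conditional. With no true effect and the same exit in both arms there is none. The sham is built to look identical and the trial is double-blind, so nothing in the documents points to exit differing by arm. The one-arm figures are a stress case.
- **That 22% to 25%, or 4.4 to 5 of 20 subjects, is the expected loss by day 60.** It is another trial's figure, used for the session criterion. Stopping sessions is not missing a remote assessment. Section 12 pays for each assessment, Section 14 offers a survey link if the phone fails, and Section 5 requires a contact person. The remark in Section 2 that "the high rate of dropout from an outpatient service after discharge from an emergency department is a challenge" concerns clinic services. Loss could be lower than assumed here.
- **That the full trial would be sized on a distorted signal.** Hypothesis 2 takes that effect size from C-SSRS intensity at the end of treatment, not from these scales at day 30 or day 60.

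It is also fair to say that loss during the ten sessions may fall before day 14. The proposed model does nothing for a subject with no post-baseline score.

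**Conclusion.** The point holds in conditional form. Section 17 gives no missing-data method, and its visit-wise t-tests leave a leaver's earlier scores out of the later comparisons. If exit follows worsening, the day 30 and day 60 differences on RRS, CAST and MADRS may be biased. At day 60 the size runs from zero, through about 0.03 to 0.08 SD (same mechanism, true 0.5 SD effect), to about 0.14 to 0.21 SD when exit follows worsening in one arm only, with no true effect or with sham-only exit. Steeper exit takes it to 0.28 SD; active-only exit with a true benefit gives less, 0.09 to 0.12. These figures rest on the assumed loss, correlations and exit models. The feasibility aim is untouched, and loss after day 14 does not touch the day 14 contrast. A change is advisable because it is cheap, not because the trial fails without it.

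**What to change.** For RRS, CAST and MADRS, replace the visit-wise t-tests in Section 17 by one likelihood-based repeated-measures model per scale:

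- terms for arm, visit and arm-by-visit;
- unstructured covariance across days 14, 30 and 60, with a simpler structure named in advance as the fallback if the model does not converge;
- small-sample degrees of freedom;
- all randomised subjects with any post-baseline score.

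Report the arm difference with its confidence interval at each visit, and tabulate the reasons for missing data by arm. State that the model relies on later missingness being explained by scores already observed, and that it cannot help subjects with no post-baseline score.

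The cost is a change of SAP wording and a little more analysis work, with a possible covariance fallback at 20 subjects. No visit, procedure or sample size changes.
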